1.5 Study Rationale

Results from Phase 2 studies and the associated open label study have shown that molindone hydrochloride extended-release (SPN-810) is safe and well tolerated in the target population of children 6-12 years of age. The goal of the phase 3 studies is to support the efficacy, safety and tolerability of SPN-810 in reducing the frequency of IA behaviors. This Phase 3 study, 810P304, is available to eligible subjects who complete the randomized, double-blind portion of one of the three Phase 3 studies, 810P301, 810P302, 810P503 or the additional Phase 2 study, 810P204. Subjects who discontinue during the maintenance phase may be allowed to participate in the OLE on a case-by-case basis only after consultation between the Investigator, the Medical Monitor and the Sponsor.

The objective of this extension study is to collect additional long-term safety data on the use of SPN-810 for the treatment of IA in subjects diagnosed with ADHD in conjunction with a standard ADHD treatment (stimulant or non-stimulant) and to collect additional data on the maintenance of the effect on IA behaviors and quality of life.

Monitoring the occurrence of any treatment emergent AEs, concomitant medications and the frequency of extrapyramidal symptoms are the primary outcome measures for this study.

In addition to safety, we will assess the severity of aggressive behaviors using the R-MOAS scale, and the severity and improvement of IA using the CGI scales. Changes in CHQ-PF28 and PSI-4-SF or SIPA scores will be used to evaluate improvement of quality of life of both the subject and the caregiver.

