4.5 Concomitant Medication

The following concomitant medications are allowed during this study:

1. Current or other FDA-approved monotherapy ADHD medication.
2. Benztropine is permitted for the treatment of emerging EPS at a starting dose of 0.5 mg BID up to a range of 1 to 4 mg/day. Lorazepam (1 to 2 mg per dose not to exceed three times daily) and clonazepam (0.25 to 1 mg per dose not to exceed twice daily) is also permitted to treat extrapyramidal symptoms.
3. For the treatment of Akathisia, propranolol is allowed up to 90 mg /day in divided doses, three times per day, starting at 10 mg BID and up to 30 mg TID, as needed.
4. Treatment for AEs other than EPS or minor transient ailments is permitted only in consultation with the Medical Monitor or his/her designee with the exception of required treatments for acute conditions in the emergency room/hospital and/or office visit as indicated.

All concomitant medications as well as the changes in the dosing of the ADHD medication or the changes to any other FDA-approved ADHD treatment will be recorded in the eCRF.

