5.1.4 Management of Treatment-Emergent EPS

If a subject experiences treatment-emergent EPS (including akathisia, dystonia, Parkinsonism, or tardive dyskinesia), benztropine will be permitted at a starting dose of 0.5 mg BID up to a range of 1 to 4 mg/day. Lorazepam (1 to 2 mg per dose not to exceed three times daily) and clonazepam (0.25 to 1 mg per dose not to exceed twice daily) will also be permitted to treat the occurrence of extrapyramidal symptoms.

For the treatment of Akathisia, propranolol is recommended up to 90 mg /day in divided doses, three times per day, starting at 10 mg BID and up to 30 mg TID, as needed.

A positive finding on an EPS safety assessment scale (Barnes Akathisia, Simpson-Angus, AIMS) does not necessarily equate to an EPS event. Investigators should evaluate positive findings on the EPS safety assessment scales and integrate them into a global clinical observation to determine if an AE of EPS should be recorded.

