6.12 Sample Size and Power Considerations

There is no consideration for power or sample size determination in this open label study. The present study is an extension to the double-blind randomized 801P301, 810P302, 810P503 and 810P204 studies for the purpose of evaluating long term safety of SPN-810.

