#### 3.4. Visit Windows

Data from scheduled visits will be analyzed. Visits will be analyzed as scheduled. Unscheduled measurements will be excluded from the descriptive statistics and statistical analyses but will be included in listings.

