# 4.5. Prior and Concomitant Medication

Prior and Concomitant medications will be coded using WHO DRUG Global version March 2019, and will be summarized descriptively by the fourth level anatomical therapeutic chemical (ATC) classification and Preferred Name (PN), using counts and percentages for the Safety Population by the optimized dose group and overall. ATC fourth (ACT4) level is for the chemical, pharmacological or therapeutic subgroup.

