# 5.6. Extrapyramidal Symptoms (EPS)

Absolute value and CFB of each item in each of EPS scales will be analyzed descriptively at each scheduled visit by the optimized dose group and overall. Data listings will be provided.

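### SAP 5.6 summarises EPS scale items only by scheduled visit, has no rule for scores taken on permitted anti-EPS drugs, and drops the protocol's any-visit worsening count without declaring it

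*SAP*

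**What the plan says.** Protocol 1.5 sets the status of the outcome: "Monitoring the occurrence of any treatment emergent AEs, concomitant medications and the frequency of extrapyramidal symptoms are the primary outcome measures for this study". SAP Table 1 lists the Simpson-Angus, Barnes and AIMS scales, and concomitant medications, under the primary safety objective.

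- **Scale analysis.** SAP 5.6: "Absolute value and CFB of each item in each of EPS scales will be analyzed descriptively at each scheduled visit", by optimized dose group and overall, plus listings.
- **Permitted treatment.** Protocol 4.5: "Benztropine is permitted for the treatment of emerging EPS". Of lorazepam and clonazepam the same section says the use "is also permitted to treat extrapyramidal symptoms". Protocol 5.1.4 adds: "For the treatment of Akathisia, propranolol is recommended up to 90 mg /day in divided doses". No duration limit is stated for any of them.
- **Unscheduled scores.** SAP 3.4: "Unscheduled measurements will be excluded from the descriptive statistics and statistical analyses but will be included in listings". SAP 3.1 agrees, except where such a value serves as baseline. For QTcF, SAP 5.4.2 does count unscheduled post-baseline assessments.
- **Any-visit worsening.** Protocol 6.8.8 plans, for each item of each scale, the number and percentage of subjects who score worse than baseline at any visit after it. SAP 5.6 does not carry this over. The only change SAP 8 names is the compliance formula.
- **Other tables.** SAP 4.5 counts prior and concomitant drugs together by ATC level 4 and preferred name. SAP 5.1 counts AESIs by system organ class and preferred term. Protocol 5.1.3.2 requires treatment-emergent EPS to be reported as an AESI.

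**The concern.** Anti-EPS drugs are given to reduce what the Simpson-Angus and Barnes scales rate. When scores on and off these drugs are averaged together, a child whose akathisia is controlled by treatment contributes the same low Barnes score as a child who never had it.

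The primary question is a per-subject frequency: how many children developed EPS, and how many needed a drug for it. Item means and changes by visit do not answer that. The protocol 6.8.8 count would have kept any worsening seen at a visit before treatment began, and it is the piece left out. At stake is whether the study can state its EPS frequency from systematic ratings, or only from what investigators chose to record as events.

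**Working it through.** The plan has no sample-size figure to reproduce ("There is no consideration for power or sample size determination in this open label study"), so the check is mainly a reading of the rules against each other.

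**1. Is there any rule for on-treatment scores?** None appears in SAP 3.1, 3.4, 3.6 or 5.6, nor in protocol 6.8.8. On-treatment and off-treatment scores are pooled.

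**2. What happens to a worsened score?** There are three routes.

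- *Worse at a scheduled visit, treated afterwards.* The score enters that visit's summary. Later visits show the treated level. Without the any-visit count, the subject is never tabulated as having worsened.
- *Symptoms between visits, treated before the next one.* Protocol 4.2 allows unscheduled visits. If a scale is rated there, the score appears only in a listing, and the next scheduled score is taken on treatment. Protocol 5.5 ties the scales to scheduled visits, so such a rating may not exist. Ratings fall at weeks 2, 4 and 8, about week 12 and month 6, then every 3 months, so this route matters mainly from Visit 5 onward.
- *Already on an anti-EPS drug at Visit 1.* Protocol 5.1.2.1 moves events ongoing from the feeder study into medical history. The baseline would then be an on-treatment score, with nothing to mark it.

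**3. What do the other tables recover?**

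| Table | Shows | Does not show |
|---|---|---|
| AESI (SAP 5.1) | EPS recorded as an event, treated or not | Positive scale findings the investigator did not record (protocol 5.1, 5.1.4) |
| Medications (SAP 4.5) | Each drug by preferred name and dose group | Indication, start relative to first OLE dose, prior versus new use, link to scores |

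**4. Illustration of scale.** Inputs are 2 subjects with EPS adverse events among the 78 in the earlier 6-month extension (protocol 1.3) and about 600 planned subjects (protocol 4.1).

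- p = 2/78 = 2.56%, matching the printed 2.6%.
- Exact (Clopper-Pearson) 95% limits: Beta(0.025; 2, 77) = 0.31% and Beta(0.975; 3, 76) = 8.96%.
- 600 × p = 15.4 subjects (1.9 to 53.7).

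Let r be the share of cases on treatment and back to baseline score at a given scheduled visit. The documents give no value for r, so the full range is shown. Visible share = p × (1 − r).

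| r (assumed) | Visible on scales at that visit | Of 600 | Of 600 at the CI limits |
|---|---|---|---|
| 0 | 2.56% | 15.4 | 1.9 to 53.7 |
| 0.25 | 1.92% | 11.5 | 1.4 to 40.3 |
| 0.5 | 1.28% | 7.7 | 0.9 to 26.9 |
| 0.75 | 0.64% | 3.8 | 0.5 to 13.4 |
| 1 | 0% | 0 | 0 |

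The expected AESI count stays at 15.4 in every row, provided the events are recorded.

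**The case against.** The strongest reply is that treated EPS is counted elsewhere. The listed drugs are permitted for EPS that someone has recognised. A child given one has been judged to have EPS and should be on the AESI form. Protocol 5.1.1 also treats a deterioration in a clinical test that leads to a change in treatment as a possible adverse event. The investigator's discretion applies mainly to raised scores not judged to be clinical EPS. This largely stands. A reader might infer that treated EPS would read as absence of EPS across the study outputs. The documents do not support that: the understatement is confined to by-visit scale summaries after treatment starts.

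A reader might also infer that no output shows use of these drugs. That is too strong, since SAP 4.5 gives each one a row by dose group. Benztropine's row should be fairly readable. Benzodiazepines are otherwise prohibited, so the ambiguity of indication falls mainly on propranolol. Prior versus new use is unclear for all four.

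A third tempting inference is that dose gradients are flattened. The documents give no anti-EPS drug use by dose, so this cannot be concluded.

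Finally, describing observed scores regardless of treatment is legitimate in a descriptive, uncontrolled study, and splitting by anti-EPS treatment conditions on the outcome. That is a good reason not to make on/off strata the main display. It does not justify dropping the protocol's any-visit count, or omitting a table of new starts.

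**Conclusion.** The point holds as a gap in the summary of a primary safety outcome and should be corrected. Three facts rest on the text alone: SAP 5.6 pools on-treatment and off-treatment scores, unscheduled scores are left out although SAP 5.4.2 counts them for QTcF, and the protocol 6.8.8 count has gone without mention in SAP 8.

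The direction, toward understating EPS on the Simpson-Angus and Barnes scales after treatment starts, assumes only that the drugs work to some degree. It is not argued for AIMS. The amount cannot be derived. The figure of about 15 subjects (2 to 54) borrows a 6-month event rate for a study of up to 60 months, and complete masking is only the extreme case r = 1. Those events, if recorded, remain in the AESI table.

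**What to change.** 1. **SAP 5.6:** restore the number and percentage of subjects with a worse score at any post-baseline visit for each item of each scale, by dose group and overall. Use each subject's worst post-baseline score and include any unscheduled ratings, as SAP 5.4.2 does for QTcF. Otherwise, declare the omission in SAP 8 with a reason.
2. **SAP 4.5:** add the number and percentage of subjects who start benztropine, propranolol, lorazepam or clonazepam on or after the first OLE dose, by dose group and overall. Limit it to EPS or akathisia use by recorded indication or, if indication is not captured (the documents do not say), by a concurrent EPS AESI.
3. **Composite:** report the number and percentage with an EPS AESI or a start of anti-EPS medication. If starts have to be identified through a concurrent AESI, this equals the AESI count by construction. In that case, also show all starts of the four drugs as an upper bound.
4. **Flag** scores taken on anti-EPS medication, including at Visit 1, in the listings. Summarise with and without them as a sensitivity analysis, not as primary strata.
5. **Reconcile** protocol 4.4, which prohibits benzodiazepines with no EPS exception, with 4.5 and 5.1.4, which permit two of them for EPS, so that the same use is not counted both as permitted treatment and as a deviation.

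The cost is SAP wording and a few tables, from data largely in hand. Some cells will be small, and the EPS figure may look less favourable. Items 1 to 4 change no treatment.

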6.8 Safety Analysis

Evaluation of safety will be performed for the safety population. Safety data that will be evaluated include concomitant medications, AEs, clinical laboratory results, vital signs, ECGs, and findings from the physical examinations. The occurrence of neurological side effects will be assessed by looking at any worsening in scores from Baseline (Visit 1) to each subsequent visit for each of the Simpson-Angus scale, Barnes Akathisia scale, and AIMS. Suicidal ideation and suicidal behavior will be measured by C-SSRS.

All summary tables related to safety analyses will use the safety population.

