6.8.8 Extrapyramidal Symptoms

The occurrence of neurological side effects will be assessed by looking at the changes in scores from Baseline to each of the post-Baseline visit for each of the Simpson-Angus scale, Barnes Akathisia scale, and AIMS. For each item on each of these scales, the number (and percentage) of subjects with a worse score at any post-Baseline visit, compared to Baseline, will be presented. A listing of these subjects will also be provided.

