# 3. GENERAL CONSIDERATIONS FOR DATA ANALYSES AND HANDLING

#### 3.1. General Statistical Methods

All statistical analysis will be performed using SAS version 9.4 or higher.

All data summaries will be presented by the optimized dose group (<18 mg/day; 18-<24 mg/day, 24-<36 mg/day or 36-54 mg/day) and overall. The optimized dose is defined as the first maintenance dose (at visit 5) for subjects entering maintenance period; otherwise using the end of study (EOS) dose for subjects discontinued prior to maintenance period.

Continuous variables will be summarized descriptively using number of subjects (n), mean, standard deviation (SD), median, minimum, and maximum.

Categorical variables will be summarized descriptively using counts and percentages. However, the number of patients with missing data will be excluded from the denominator for the percentage calculation. When the denominator for the percentage is different from the number of subjects in the treatment column header, the denominator will be clearly specified in the table or in a footnote for the table.

Individual subject data will be listed by subject ID. Unscheduled measurements (unless defined as baseline) will be excluded from summary tables but will be included in data listings. For assessments that are repeated or unscheduled, unless otherwise specified, the non-missing values from the first assessment will be used for generating summary statistics.

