#### 5.6.1. Simpson-Augus Scale

The Simpson-Angus scale is a 10-item rating scale that is widely used for assessment of neuroleptic-induced Parkinsonism. It consists of 1 item measuring gait, 6 items measuring rigidity, and 3 items measuring glabella tap, tremor and salivation, respectively.

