#### 5.6.2. Barnes Akathisia Scale

The Barnes Akathisia scale is a rating scale for drug-induced akathisia and includes components for rating the observable, restless movements characteristic of akathisia, the awareness of restlessness, and any distress associated with the condition.

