#### 5.6.3. Abnormal Involuntary Movement Scale (AIMS)

The AIMS test is a rating scale used to measure tardive dyskinesia. There are 12 items that rate involuntary movements of various areas of the subject's body.

SPN-810

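### SAP 5.6 summarises the EPS scales item by item only, so its tables (though not its by-subject listings) cannot show whether worsening clusters within a child

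*SAP*

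**What the plan says.** SAP 5.6 sets the unit of analysis for the Simpson-Angus, Barnes and AIMS scales: "Absolute value and CFB of each item in each of EPS scales will be analyzed descriptively at each scheduled visit", by optimized dose group and overall. It then adds: "Data listings will be provided". The statistics come from SAP 3.1: "Continuous variables will be summarized descriptively using number of subjects (n), mean, standard deviation (SD), median, minimum, and maximum".

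SAP 5.6.1 to 5.6.3 describe the instruments. On Simpson-Angus: "It consists of 1 item measuring gait, 6 items measuring rigidity, and 3 items measuring glabella tap, tremor and salivation, respectively". On AIMS: "There are 12 items that rate involuntary movements of various areas of the subject's body". On Barnes: "The Barnes Akathisia scale is a rating scale for drug-induced akathisia and includes components for rating the observable, restless movements characteristic of akathisia". None of the three subsections defines a total, mean or global score.

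Protocol 6.8 plans to judge neurological side effects by "looking at any worsening in scores from Baseline (Visit 1) to each subsequent visit for each of the Simpson-Angus scale" and likewise for the other two scales. Protocol 6.8.8 says they will be "assessed by looking at the changes in scores from Baseline to each of the post-Baseline visit for each of the Simpson-Angus scale" and the other two. It then asks, item by item, for the number and percentage of subjects who are worse at any visit after baseline, with a listing of those subjects.

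Elsewhere the SAP does work at the level of a score or a subject. Sections 7.1 to 7.3 give full scoring for CHQ-PF28, PSI-4-SF and SIPA, section 6.1 uses an R-MOAS total, and section 5.4.2 counts subjects with a notable QTcF.

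**The concern.** SAP Table 1 lists the EPS scales under the primary safety objective, and Protocol 1.5 names the frequency of extrapyramidal symptoms among the primary outcome measures. A reader of the safety results will ask how many children got worse on a scale, and by how much. Tables of item means and ranges answer neither question.

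Each item is summarised across children separately from every other item, so the link between items within a child disappears from the tables. One child whose gait, rigidity and tremor all worsen together is a different safety message from several children with one isolated one-point change each. The item tables can look the same for both. The exploratory questionnaires receive full scoring, while the primary safety scales receive neither a score nor a subject count.

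**Working it through.** The plan states no figure to reproduce here. The check is whether the planned item statistics can tell two plainly different situations apart.

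**Inputs**
- Items: 10 on Simpson-Angus (SAP 5.6.1).
- Statistics: n, mean, SD, median, minimum, maximum (SAP 3.1).
- N = 600, the approximate planned enrolment (Protocol 4.1), and N = 100 as an assumed dose-group size.
- Assumptions for illustration: one visit, all baseline item scores 0, an increase means worsening, no missing items.

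**Two cases**
- A: one child changes by +1 on six items.
- B: six children change by +1, each on a different one of those six items.

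**Item level.** In both cases each affected item has a single child at +1 and N − 1 children at 0. Hence:
- mean = 1/N, which is 0.00167 at N = 600 and 0.01 at N = 100;
- variance = (1 − 1/N)/(N − 1) = 1/N, so SD = 1/√N, which is 0.0408 and 0.100;
- median 0, minimum 0, maximum 1;
- children worse on that item: 1.

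The four unaffected items are all zeros in both cases. Every planned item statistic is therefore identical for A and B at either N. With baseline at 0, the tables of absolute values match too.

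**Per-subject total (sum of the 10 items).** The sum of total changes is 6 in both cases, so the mean is 6/N. The variance differs:
- A: (36 − 36/N)/(N − 1) = 36/N, so SD = 6/√N.
- B: (6 − 36/N)/(N − 1). At N = 600 this is (6 − 0.06)/599 = 0.00992, so SD = 0.0996. At N = 100 it is (6 − 0.36)/99 = 0.0570, so SD = 0.239.

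| | A, N=600 | B, N=600 | A, N=100 | B, N=100 |
|---|---|---|---|---|
| Mean total change | 0.010 | 0.010 | 0.06 | 0.06 |
| SD | 0.245 | 0.0996 | 0.600 | 0.239 |
| Maximum | 6 | 1 | 6 | 1 |
| Children with any worsening | 1 (0.17%) | 6 (1.0%) | 1 (1%) | 6 (6%) |

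Two things follow. First, the mean total does not separate the cases. The SD, the maximum and above all the subject count do. Second, the per-item worsening counts of Protocol 6.8.8 would not separate them either, because they show one child per item in both cases. Their absence from SAP 5.6 is a different gap, and restoring them would not close this one.

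**The case against.** **Listings.** The strongest reply is that the data are not hidden. SAP 5.6 promises listings, and SAP 3.1 lists individual data by subject, so anyone reading them can see which items moved in which child. This stands. A reader might infer that the two cases cannot be distinguished in any planned output, and that would be wrong: the limitation is in the summary tables. Still, listings for about 600 subjects over up to 24 post-baseline visits are not a reported result by dose group.

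**Departure from the protocol.** A reader might also infer that the SAP has dropped a scale-level analysis the protocol required, without declaring it in SAP section 8. The text does not establish this. Protocol 6.8 and 6.8.8 speak of changes in scores for each scale, which can be read as scale-level, especially since 6.8.8 goes on to introduce items separately. But neither section names a total, and the only output specified in detail is by item. Scores may simply mean item scores.

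**Size of the output.** Counting 10 + 12 + 3 items (the three Barnes components being inferred from its description), 24 visits and 5 columns gives 25 × 24 × 5 = 3,000 mean changes. That is table volume. It does not show that a signal would be missed.

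**Adverse events.** Protocol 5.1.3.2 has EPS reported as events of special interest, and SAP 5.1 tabulates these by number and percent of subjects, so EPS does have one subject-level summary. It does not fill this gap, because Protocol 5.1.4 says a positive scale finding need not be an EPS event. That table reflects investigator judgement, not the scale ratings themselves.

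**Scoring.** The documents do not say how AIMS or Barnes should be scored, as the forms are in the Investigator Site File. This also stands, and it limits how specific the fix can be.

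**Conclusion.** The point holds for the summary tables. SAP 5.6 gives a primary safety endpoint no per-subject scale score and no count of subjects with any worsening, and its item statistics are exactly equal in the two cases above. At N = 600 the missing subject-level results would be a maximum change of 6 against 1, and 0.17% against 1.0% of children with any worsening. The equality of the item tables does not depend on N. The example is constructed: it shows what the tables cannot reveal and says nothing about how often such clustering will occur.

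The point does not extend to the listings, which keep the information, and it does not rest on an undeclared protocol departure, which the wording leaves open. This is a descriptive study without a power calculation (Protocol 6.12), so no test or error rate is affected. What is at stake is whether the report can say how many children worsened on each scale and how far.

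**What to change.** In SAP 5.6:
1. Derive one score per subject, visit and scale. For Simpson-Angus use the sum of the 10 items. For AIMS and Barnes use the score defined by the instrument in the Investigator Site File, and write that definition into the SAP.
2. Summarise the value and its change from baseline by visit, by optimized dose group and overall.
3. For each scale, report each subject's maximum post-baseline change and the n (%) of subjects with any worsening from baseline. These carry the information that the mean total does not.
4. State how a missing item affects the score, since the rule in SAP 3.6 covers efficacy variables only.
5. Keep the item tables as supporting output, and record the addition in SAP section 8.

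Cost: SAP text, three derived variables and a few extra tables. The item ratings are already scheduled at every visit, so no new data collection is needed. Total output rises slightly because the item tables stay.
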